Specify your research question(s), study aims or hypotheses (do not indicate "see protocol")

Surgical site infections are a subset of healthcare-associated infections (HAIs) that affect 3-5% of all patients undergoing surgery and are associated with a 2-fold increase in patient morbidity and mortality, a 2-fold increase in hospital duration, and a 66% increase in the risk of intensive care unit (ICU) admission (1-4). The Centers for Disease Control (CDC) and the World Health Organization (WHO) consider HAIs as a devastating issue tied to antibiotic resistance and have highlighted three major goals for HAI prevention including the following: 1) Prevention of infections in patients undergoing surgery, 2) Prevention of patient-to-patient bacterial transmission, and 3) improvement in antibiotic stewardship (5-7). These recommendations apply to the perioperative arena where the contribution of intraoperative bacterial reservoirs to bacterial transmission events and postoperative infection development has been confirmed (8-10). Indeed, a multicenter study recently demonstrated that stopcock contamination occurred in 23% of surgical cases, was associated with increased mortality, and was linked by molecular typing to postoperative infection (9). Intraoperative bacterial reservoir isolates have also been directly linked to the causative organism of infection for 30% of 30-day postoperative HAIs. Finally, transmission of S. aureus has been confirmed in up to 39% of surgical cases and has been directly linked to postoperative infection development(11). As such, attenuation of perioperative S. aureus transmission is an important target for HAI reduction. Therefore, our primary objective is to reduce perioperative S. aureus transmission. Our

secondary objective is to examine the impact of reduced *S. aureus* transmission on the incidence of superficial and deep surgical site infections (SSIs).

I.6 ***Background and significance and/or Preliminary studies related to this project. (do not indicate "see protocol")***

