Sample Processing: All samples will be sent to RDB Bioinformatics for processing. Results will be entered into the software. The software will guide testing to identify *S. aureus* transmission events. *S. aureus* transmission events will be processed to identify transmission stories, and transmission stories will be reported in the software platform to guide proactive improvements in the bundle.

Infection Tracking: The patient will be followed for 90 days postoperatively to identify and infection. Initial screening criteria will include an elevated white blood cell count, fever ($T > 38$ degrees), anti-infection order, culture, or office documentation of infection. If one or more criteria are present, the patient will undergo a full chart review to determine if they developed a healthcare-associated infection (HAI) as determined by National Healthcare Safety Network (NHSN) definitions. All patient cultures obtained for infectious workup by the usual healthcare teams will be saved by the clinical microbiology laboratory. Samples will be sent to RDB for analysis in order to determine if the organism was clonally-related to an organism isolated from one or more reservoirs during the perioperative period.

Confounding Factor Analysis: Information from the patient medical record will be collected by the study team: date and time of surgery, diagnosis, ASA status (a system for assessing the fitness of patients before surgery), age, comorbidities (the presence of one or more additional diseases or disorders co-occurring with (that is, concomitant or concurrent with) a primary disease or disorder), surgery type and duration, type of anesthesia provided, operating room number, gender, dirty or infected surgery (yes/no), preoperative location, postoperative location, and duration of anesthesia. Data will password protected and kept in microEMR.

All patients will be called at 90 days (Up to 3 attempts will be made) to determine if they developed an infection.

VII.E.7 *Will you attempt to recontact subjects who are lost to follow-up?*

No - those lost to followup will not be recontacted

VII.E.9 *Will subjects be provided any compensation for participating in this study?*

No

VIII. Risks

VIII.1 *What are the risks to subjects including*

- emotional or psychological

- financial

- legal or social

- physical?

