Reducing Perioperative S. aureus Transmission via use of an Evidence-Based, Multimodal Program Driven by an Innovative Software Platform (OR PathTrac)

9/20/2018

Statistical Analysis

Multiple statistical methods were used. For simplification, we list the statistical methods in the precise sequence they are reported in the results.

The Fisher exact test was used to compare patient and procedural demographic information for treatment vs control groups and for cases involving *S* aureus transmission. Similarly, the distribution of patients by ASA scores greater than 2 and by sex for enrolled vs eligible patients were compared by surgeon using the Mantel-Haenszel test.

The Fisher exact test was also used to examine the potential association of each of the covariates mentioned earlier with *S aureus* transmission. None were associated.

A 2-sided Wilcoxon-Mann-Whitney test was used to examine the association of treatment assignment with the number of transmitted *S aureus* isolates. Poisson regression was used to estimate the incidence risk ratio (IRR) of *S aureus* transmission for the independent variable of treatment. Poisson regression was used to estimate the IRR because the incidence of transmission was so large (ie, much greater than 10%) that the odds ratio estimated using logistic regression would be a biased estimator of the relative risk.²⁴ We repeated the analysis using multilevel Poisson regression clustering by surgeon or specialty.

The Fisher exact test was used to compare the proportion of patients in the treatment group with transmission events before vs after surveillance feedback and the proportion of patients with SSI with and without documented *S aureus* transmission. Poisson regression was used to compare the proportion of patients with SSI with and without documented *S aureus* transmission, clustered by surgeon.

The proportion of patients with SSIs was compared with the Fisher exact test. Time to infection was evaluated by Cox proportional hazard modeling. We repeated the analysis using multilevel Poisson regression clustering by surgeon and specialty.

There were no missing data for the primary and secondary outcomes. Calculations were performed using Stata version 16.1 (StataCorp). All P values were 2-sided, and P < .05 was taken to indicate statistical significance.

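### The SAP relates S. aureus transmission to SSI of any organism and never uses the planned typing of infection isolates, so a true link may be diluted and a positive one cannot be told apart from general case risk

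*SAP*

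**What the plan says.** The SAP (Statistical Analysis) compares SSI between patients with and without documented S. aureus transmission twice. The first comparison is a Fisher exact test. The second is described as "Poisson regression was used to compare the proportion of patients with SSI with and without documented" S. aureus transmission, clustered by surgeon. A separate sentence reads "The proportion of patients with SSIs was compared with the Fisher exact test". None of these sentences limits SSI by organism, and none refers to the organism cultured or to a clonal match.

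The protocol plans to collect that information. Under Infection Tracking in VII.E.6 it states "All patient cultures obtained for infectious workup by the usual healthcare teams will be saved by the clinical microbiology laboratory", and that samples go for analysis to "determine if the organism was clonally-related to an organism isolated from one or more reservoirs during the perioperative period". An earlier paragraph of VII.E.6 describes the same step for positive cultures found on chart review.

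The secondary objective in I.5 concerns the impact of reduced S. aureus "transmission on the incidence of superficial and deep surgical site infections". It sets no limit by organism.

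**The concern.** A transmitted S. aureus isolate can directly cause only an S. aureus infection. SSIs from other organisms enter the outcome as events which that mechanism cannot explain, and they pull a true risk ratio towards 1.

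A positive result would be ambiguous as well. Protocol XI.2 lists case duration over 2 hours and discharge location among the variables known to be associated with transmission, and longer or more complex cases could plausibly carry more infection of every kind. The SAP describes this Poisson model as clustered by surgeon and names no covariate. An association with any-organism SSI could therefore reflect S. aureus causation or simply a riskier case. Isolate typing is the planned information best suited to separating the two, and it has no place in the analysis.

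**Working it through.** **No stated figure to reproduce.** The documents give no power, event count or effect size for any SSI analysis. As a check of the formula, the primary-endpoint case in XI.2 (40% v 28%, 500 per arm, no variation between lines, stated power 98%) comes out at 98.0%.

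**Inputs from the documents.**
- Patients: 1,000 case pairs, so 2,000 patients (XI.1).
- SSI risk q = 4%, the middle of the 3-5% in I.5.
- Exposed fraction e = 34%, the mean of the 40% and 28% planning rates in XI.2.
- Test: two-sided, alpha 0.05 (SAP).

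**Assumptions not in the documents.** S. aureus share of SSIs s = 20-50%; true risk ratio for S. aureus SSI r = 3; no effect of transmission on SSI from other organisms; every S. aureus SSI cultured; no clustering.

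**Formulas.**
- S. aureus SSI, unexposed: a0 = s·q / (1 − e + e·r). Exposed: a1 = r·a0.
- Other-organism SSI in both groups: b = q·(1 − s).
- Any-SSI risk ratio: (a1 + b) / (a0 + b).
- Power = Φ[(d − 1.96·SE0) / SE1], where d is the risk difference, SE0 the pooled and SE1 the unpooled standard error, with 680 exposed and 1,320 unexposed.

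**Worked case, s = 30%.** a0 = 0.012 / (0.66 + 1.02) = 0.71%; a1 = 2.14%; b = 2.8%. Any SSI is 4.94% v 3.51%, a risk ratio of 1.41 in place of 3.
- Any SSI: (0.01429 − 1.96 × 0.00925) / 0.00974 = −0.39, power 35%.
- S. aureus SSI: (0.01429 − 1.96 × 0.00514) / 0.00602 = 0.70, power 76%.

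| S. aureus share | Any-SSI risk ratio | Power, any SSI | Power, S. aureus SSI |
|---|---|---|---|
| 20% | 1.26 | 18% | 60% |
| 30% | 1.41 | 35% | 76% |
| 40% | 1.57 | 54% | 86% |
| 50% | 1.75 | 71% | 92% |

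At a 30% share, a true risk ratio of 2 gives 17% v 42%. With 1,000 first patients only, risk ratio 3 and a 30% share, power is 20% v 50%.

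**Second set of inputs** (1,000 patients, SSI 5%, 39% exposed as in I.5, risk ratio 3): 13% v 42%, 23% v 56%, 51% v 77% and 78% v 89% at shares of 20%, 30%, 50% and 70%. The direction is the same and the gap narrows as the share rises.

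**Where the gain disappears or reverses** (2,000 patients, 34% exposed, SSI 4%, risk ratio 3 for S. aureus):
- Half of S. aureus SSIs cultured: any SSI 35% v S. aureus SSI 50% at a 30% share; 71% v 69% at a 50% share.
- All cultured, 30% share, transmission also associated with other-organism SSI: 79% v 76% at a ratio of 1.5; 95% v 76% at a ratio of 2. Part of that any-SSI power would be detecting shared case risk, not S. aureus causation.

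**Expected S. aureus SSIs at a 30% share:** 2,000 × 0.04 × 0.30 = 24, or 12 among 1,000 first patients.

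**The case against.** The strongest reply is that the SAP analyses what the protocol asked for. The objective in I.5 covers superficial and deep SSIs without naming an organism, so any-organism SSI is the matching endpoint. That stands: the endpoint is not an error and should not be displaced.

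A reader might also infer from the lower rows of the table that most of the power for this objective is lost. The documents do not support that. They give neither the S. aureus share of SSIs, nor the risk ratio, nor the fraction of SSIs cultured, and they state no SSI power that could be lost. The 30% in I.5 is the proportion of postoperative HAIs linked to a reservoir isolate, for any organism; it is not an S. aureus share of SSI. At a 40% or 50% share the loss is well under half, and the reversal cases show that the sign is not secure.

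Incomplete culturing is a real limit. Only cultures taken by the usual care teams are saved, and an anti-infection order or office documentation can trigger the review that identifies an infection, so some SSIs will have no isolate. Scoring those as non-events in an S. aureus-only outcome would introduce misclassification of its own.

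On confounding, the SAP reports that none of the tested covariates was associated with transmission and clusters the model by surgeon. This weakens the concern without removing it: absence of a detected association does not exclude shared risk, and clustering by surgeon does not adjust for case complexity.

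Finally, the SAP is written in the past tense and reports findings, so replacing the outcome now would change it after analysis. That also stands, and it argues for addition over replacement.

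**Conclusion.** The gap holds on the text alone: the exposure is organism-specific, the outcome is not, and the planned isolate typing feeds no analysis. If transmission acts only on S. aureus SSI, the any-SSI risk ratio is diluted, for example from 3 to between 1.26 and 1.75 at shares of 20-50%, with any-SSI power of 18-71% against 60-92% for S. aureus SSI. Those figures rest on 2,000 patients, 34% exposed, 4% SSI, complete culturing, no clustering and no relation between transmission and other-organism SSI; the true amount cannot be fixed from the documents.

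The interpretive weakness depends on none of these assumptions. Without the split by organism, a positive comparison cannot distinguish S. aureus causation from general case risk or general contamination. The point therefore warrants added supportive analyses, not a change of endpoint.

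**What to change.** Keep any-organism SSI as the analysis for the stated objective, and leave the between-arm SSI comparison as it is. Beside the existing Fisher and Poisson comparison by transmission status, add the following, labelled as supportive and as added to the plan:

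- (a) SSI with S. aureus cultured.
- (b) Among those, the number whose isolate clonally matches a perioperative reservoir isolate.
- (c) SSI with a culture but no S. aureus, as a negative-control outcome. A similar association here would point to general case risk or contamination.
- SSIs without a culture reported as their own category by transmission status, not counted as non-events.

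The cost is SAP wording and a few extra models on data the protocol already plans to collect. The downside is sparse events (about 24 S. aureus SSIs in 2,000 patients at an assumed 30% share, fewer with incomplete culturing), so these analyses can support or qualify the any-SSI result but cannot carry the conclusion alone.

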Surgical service lines will include orthopedic total joint, orthopedic spine, gynecology/oncology, thoracic, general, hernia, colorectal, open vascular, plastic, and open urological procedures. These lines will be randomized 1:1 to either the bundle of activities or usual care. The unit of randomization is the service line. The perioperative environment (the patient, the patient to follow, and all providers caring for the patient and the patient to follow) for the randomized service line (treatment or usual care) will be involved in surveillance. This means that all patients, all providers caring for those patients (changes day by day), and care environments (equipment and stopcock sets) will be involved in surveillance. Surveillance from treatment and control groups will yield *S. aureus* transmission events that will be processed to guide proactive improvements in the treatment bundle.

Treatment group (bundle) inclusion/exclusion criteria:

Inclusion criteria: Patients seen at UIHC who are scheduled to undergo surgery from providers in one of the service lines above, documentation of informed, written consent, >18 years of age, procedure requiring general/regional anesthesia.

Exclusion criteria: Lack of documented informed, written consent, patients <18 years of age, procedures outside of the surgical service lines listed above, not requiring general/regional anesthesia, patients not seen in the UIHC clinics, and an allergy to iodine/shellfish or chlorhexidine.

Usual care group (existing practice at UIHC) inclusion/exclusion criteria:

Inclusion criteria: Patients seen at UIHC who are scheduled to undergo surgery from providers in one of the service lines above, documentation of informed, written consent, >18 years of age, procedure requiring general/regional anesthesia.

Exclusion criteria: Lack of documented informed, written consent, patients <18 years of age, procedures outside of the surgical service lines listed above, not requiring general/regional anesthesia, patients not seen at UIHC, and an allergy to iodine/shellfish or chlorhexidine.

VI.14

Provide an estimate of the total number of subjects that would be eligible for inclusion in each of your study populations (include your control population if applicable)

We anticipate that >80% of all patients undergoing surgery in the surgical service lines above will be eligible for the study.

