Kits will be transported to RDB Bioinformatics laboratory for processing following sample acquisition. The dynamic surveillance software platform will guide proven, systematic phenotypic and genomic processing of collected samples in order to identify clonal transmission events occurring within and between operating room reservoirs in the observational unit (case pair). Guidance will be based on the strength of epidemiological-relatedness as follows: A transmission event will be defined as the presence of one or more isolates in a measured reservoir that was not present at case start. Transmission events within an observational unit will be further analyzed as directed by the RDB platform to identify clonally-related *S. aureus* transmission events.

The RDB Bioinformatics software platform will process transmission dynamics in order to continually summarize the epidemiology of *S. aureus* transmission. This information will be continually displayed in order to identify the most common reservoir of origin, the most common transmission locations (vectors), the most common mode of transmission (vertical or horizontal), and involvement of key portals of entry (stopcocks). To address strain characteristics, reports will focus on more pathogenic strains defined by the top 5 most transmissible, resistant, and virulent strain characteristics.

Automated analysis reports for overall transmission and for transmission of more pathogenic strains will be used by the infection control perioperative team to continually optimize the interventions affecting all patients in the treatment clusters as described further below. The platform will automatically quantify transmission events occurring in

treatment and control clusters such that involved in data collection and data entry will be blinded to the primary outcome.

All data will be analyzed by the statistician ([name]) at Dartmouth Hitchcock Medical Center who will not be involved in data collection.

Work flow: Monday-Friday only. Limited to patients that are seen in UIHC clinics. 1,000 case pairs: (500 treatment and 500 usual care) will be studied during the 2-year study period. This corresponds to one case pair in the “bundle” group and one case pair in the usual care group each day (5 days a week for 50 weeks each year). All patients will be followed for 90 days for infection development.

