 - Improved environmental cleaning: Environments (OR and ward) affected by high-risk S. aureus transmission events will be mapped by surveillance and addressed by automated reporting to the anesthesia workroom supervisor. This will trigger improvements in routine (standard cleaning using quaternary ammonium compound and micro cloth followed by a surface disinfection wipe) and terminal [improved routine technique followed by employment of robotic cleaning (Ultraviolet light)] cleaning.
- Fatigue mitigation: The team will use surveillance to continually monitor the impact and fatigue of the proposed interventions as conveyed by failure mode analysis of transmission dynamics involved clonal S. aureus transmission.

XI.2

Provide the rationale or power analysis to support the number of subjects proposed to complete this study.

Statistical Analysis: The unadjusted primary intention to treat analysis will compare the proportion of clonally-related S. aureus transmission events occurring in treatment vs. control perioperative (preoperative, intraoperative case pair, and postoperative) observational units across the 6 randomized service lines using the Chi squared test. We will assess for balance for variables known to be associated with intraoperative

transmission (case, duration > 2 hours, and discharge location). In the case of imbalance, we will use multivariate techniques to further explore the treatment effect using a generalized linear models approach.

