Initial Power Analysis (see amendment below based on reviewer concerns): We intend to screen a total of 1000 patients for up to 10 surgical service lines. Service lines will be randomized 1:1, yielding 500 patients in each treatment arm. Each patient will provide 4 observational units that include preoperative to intraoperative, intraoperative case 1 to intraoperative case 2, intraoperative case 1 to postoperative, and preoperative to postoperative opportunities for detection of *S. aureus* transmission. Thus, 500 patients in each arm will provide 2,000 observational units for a total of 4,000 observational units during the two-year study period. We originally calculated that this provided 90% power to detect a 30% relative reduction in the primary outcome (10.58% down to 7.41%). The estimated clonally related *S. aureus* transmission rate was based on a previously reported detection rate of 58 events in 548 observational units for all-comers to the operating room at 3 major academic medical centers in the United States. To address service line variation, we supposed that the logit-frequencies of the primary outcome for each service line were distributed as a normal distribution with a mean of -0.41 and standard deviation of 0.20. This amount of between-line variation corresponds to an intra-cluster correlation (ICC) of approximately 1%. It can also be interpreted as the amount of variation in which service lines in the top quartile of rates would have an average frequency (after removing within subsection binomial variation) of 46% while service lines in the lowest quartile have an average frequency of 33%. These calculations were accomplished using Monte Carlo simulations written in R 3.3, and using in part the following approximation for the ICC when rates are logit-normal, $1/(1+1/\sigma^2 \cdot \pi^2 \cdot \text{pa}(1-\text{pa}))$ (which can be readily derived using the delta theorem) where pa is the average frequency across centers and σ^2 is the standard deviation on the logit scale. We calculated that this provides 85% power to detect a 30% relative reduction in the primary outcome (40% down to 28%) if there is significant variation between service lines. If indeed there is no variation between service lines, the power is 98%.

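### The SSI Cox model has no stated allowance for the randomised service lines, and the SAP does not say which SSI result is interpreted

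*SAP*

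**What the plan says.** Protocol VI.13 states that "The unit of randomization is the service line" and that "These lines will be randomized 1:1 to either the bundle of activities or usual care". Protocol I.5 makes the incidence of superficial and deep SSI the secondary objective.

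For SSI by arm, the SAP lists three analyses in consecutive sentences:

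- A test of proportions: "The proportion of patients with SSIs was compared with the Fisher exact test".
- A time-to-event model: "Time to infection was evaluated by Cox proportional hazard modeling".
- A repeat of the analysis by multilevel Poisson regression, clustered by surgeon and specialty.

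The first two carry no cluster term. The SAP does not say whether the repeat covers the Fisher comparison, the Cox comparison or both. It does not relate specialty to the randomised line, and it names no SSI result as decisive. Its only decision rule is two-sided P < .05.

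The number of lines is not settled. Protocol XI.2 refers in its analysis paragraph to a comparison "across the 6 randomized service lines", and in its power paragraph says "We intend to screen a total of 1000 patients for up to 10 surgical service lines".

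**The concern.** When whole service lines are allocated, patients in one line share procedures, surgeons and baseline infection risk. If SSI rates differ between lines for reasons unrelated to the bundle, a chance imbalance in which lines fall in which arm looks like a treatment effect. A model that counts patients as independent then gives too small a standard error.

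The protocol accepts this for transmission: XI.2 models variation between lines and reports power of 85% with it and 98% without. Nothing equivalent is stated for SSI. Elsewhere the SAP says explicitly when a model is clustered, so the absence of any such term on the Cox model cannot be read as implied clustering. With no SSI result designated, a significant unclustered hazard ratio could be reported as the SSI effect even if the clustered model disagreed.

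**Working it through.** **Inputs.** 500 first patients per arm (Protocol XI.2: "Service lines will be randomized 1:1, yielding 500 patients in each treatment arm"). Lines: 10 or 6 (XI.2), so about 100 or 167 first patients per line. Between-line SD on the logit scale: 0.20 (XI.2, for transmission). SSI rate: 3-5% (I.5). Assumption not in the documents: SD 0.50, to show the range.

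**1. Reproduce the protocol's figures.** For 40% vs 28% with 500 per arm, the pooled rate is 0.34. The null SE is √(2×0.34×0.66/500) = 0.02996 and the alternative SE is √((0.24+0.2016)/500) = 0.02972. Then z = (0.12 − 1.96×0.02996)/0.02972 = 2.06, so power is 0.980, matching 98%. With ICC = σ²p(1−p)/(1+σ²p(1−p)), σ = 0.20 and p = 0.40, ICC = 0.0096/1.0096 = 0.0095, matching the stated 1% or so.

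**2. Carry the same SD to SSI.** At p = 0.04, p(1−p) = 0.0384.

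- SD 0.20: ICC = 0.001536/1.001536 = 0.0015.
- SD 0.50: ICC = 0.0096/1.0096 = 0.0095.

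Design effect DE = 1+(m−1)×ICC. Real two-sided error of a nominal 5% test = 2×(1−Φ(1.96/√DE)).

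| SD | Lines (m) | DE | Error |
|---|---|---|---|
| 0.20 | 10 (100) | 1.15 | 6.8% |
| 0.20 | 6 (167) | 1.25 | 8.0% |
| 0.50 | 10 (100) | 1.94 | 16% |
| 0.50 | 6 (167) | 2.58 | 22% |

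**3. Check by simulation.** The formula assumes a test that starts at exactly 5%, which Fisher's does not. Line rates were therefore simulated as logit-normal with no treatment effect (20,000 runs per setting), at SSI rates of 3% and 5%. Cox was approximated by the rare-event log-rank score statistic.

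| SD | Lines | Cox error | Fisher error |
|---|---|---|---|
| 0 | 10 | 0.040-0.049 | 0.032-0.033 |
| 0 | 6 | 0.042-0.051 | 0.035 |
| 0.20 | 10 | 0.061-0.064 | 0.044-0.055 |
| 0.20 | 6 | 0.072-0.077 | 0.054-0.068 |
| 0.50 | 10 | 0.141-0.183 | 0.117-0.168 |
| 0.50 | 6 | 0.192-0.262 | 0.166-0.245 |

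**4. Which patients count.** XI.1 says "All patients will be followed for 90 days for infection development", so second patients of each pair may also enter. With 1000 per arm and SD 0.20, the simulated error across 10 and 6 lines is 0.074-0.115 for Cox and 0.061-0.105 for Fisher.

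**5. Few clusters.** With lines minus 2 degrees of freedom, the 5% critical value is 2.31 for 10 lines (8 df) and 2.78 for 6 (4 df), against 1.96. The SAP states no small-sample correction, so the multilevel Poisson interval may also be too narrow.

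**6. Permutation limits.** Ten lines split 5:5 give C(10,5) = 252 allocations and a smallest two-sided p of 2/252 = 0.008. Six split 3:3 give C(6,3) = 20 and 2/20 = 0.10.

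**The case against.** A reader might infer that the SSI comparison as a whole ignores clustering. The documents do not support that. The sentence after the Cox model describes a multilevel Poisson repeat, which is the direct clustered counterpart of the Fisher comparison and estimates the incidence contrast named in the secondary objective. With about 4% events, a 90-day window and no missing secondary outcome data according to the SAP, the risk ratio and hazard ratio should be close. The missing clustered interval for the hazard ratio is therefore a limited gap. That much stands. It still leaves the hazard ratio without a valid stated interval of its own, and the choice between results open.

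A reader might also infer that both unclustered p-values are certainly and seriously too small. That too goes further than the documents. They give no SSI ICC, and at the protocol's own SD the Cox inflation is small. Fisher's conservatism offsets it with 10 lines and first patients only. Errors of 14% and above for 500 per arm need the assumed SD of 0.50.

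The pilot contrast in XI.2 (28% orthopaedic, 58% gyn/onc) suggests lines can differ by more than SD 0.20. But it concerns two lines and transmission not yet confirmed as clonal, so it cannot fix the SSI value.

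Finally, the Fisher test of SSI by transmission status does not compare randomised arms and is outside this point.

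**Conclusion.** The point holds in a limited form. The Cox model for SSI, as stated, treats patients as independent although lines were randomised, so its interval is too narrow to the extent that SSI rates vary between lines. With 500 first patients per arm, the type I error is about 6-7% (10 lines) or 7-8% (6 lines) if the transmission SD of 0.20 applies to SSI. It would be about 14-18% or 19-26% if the SD were 0.50, which is an assumption. Fisher is near nominal in the mildest of these settings and is already paired with a clustered model. The remaining defect is one of designation and definition: which SSI result is interpreted, whether the repeat covers the Cox model, whether specialty is the randomised line, and what inference is used with so few lines. This is a secondary outcome and the correction is worth making. Nothing here shows that a reported SSI effect would be false.

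**What to change.** 1. Reconcile the 6 lines with the up to 10 lines in Protocol XI.2, because the design effect, degrees of freedom and any permutation test depend on it. State whether second patients enter the SSI analysis.
2. Fit the Cox model with a shared frailty for service line or line-clustered variance, with small-sample inference: t on lines minus 2 df, critical value 2.31 for 10 lines or 2.78 for 6.
3. Define specialty as the randomised line and say which analyses the multilevel Poisson repeat covers.
4. Name the line-level SSI result as the one interpreted. Label the Fisher test by arm and the unclustered Cox model descriptive.
5. Use a permutation p-value only if there are enough lines. With 10 it can reach 0.008. With 6 it cannot go below 0.10, so it could never meet P < .05.

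Cost: SAP wording and a model option. Because the SAP reports analyses in the past tense, it probably also means a re-run. Intervals will be wider, and precision will be low whichever model is used: 4% of 1000 first patients is about 40 events, or roughly 4 per line with 10 lines and 7 with 6. A frailty variance will be poorly estimated, and line-clustered variance needs the small-sample correction.
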